We will only collect information that is essential for the purpose of the research. Research data is treated as confidential and will be identifiable only via ID numbers. The key linking ID numbers with individuals will be stored securely and separately from the research data, and accessible only by authorised individuals in the research team.

The privacy of personal data is paramount and will not be disclosed unless there is a justified purpose for doing so. The University NEVER sells personal data to third parties. Data may be shared with:

- Immediate project team who are authorised to work on the project and access the information. This may include staff at Sheffield Hallam University or collaborators at other organisations authorised to work on the project. This will be clearly identified in the information sheet. Our research may be audited and access to the data may be required. The University puts in place safeguards to ensure that audits are conducted in a secure and confidential manner.
- In the case of complaints about a research project the Head of Research Ethics may require access to the data as part of our Research Misconduct Procedure.

The University takes a robust approach to protecting the information it holds with dedicated storage areas for research data with controlled access. For particularly sensitive projects the University puts into place additional layers of security. The University has a high level of data security and follows the NCSC "10 Steps to Cyber Security" framework to structure security planning and operations. Through information strategy, policy and process the University is aligning to the ISO27001 standard. Alongside these technical measures there are comprehensive and effective policies and processes in place to ensure that users and administrators of University information are aware of their obligations and responsibilities for the data they have access to. By default, people are only granted access to the information they require to perform their duties. Training is provided to new staff joining the University and existing staff have training and expert advice available if needed.

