To address not only whether the intervention works, but also how the intervention works, we will also test the exploratory mediation models depicted in Figure 1 and Figure 2.

RQ9 Is the effect of MBT-PP (compared to TAU) on externalising and internalising behaviours in children aged 8-14 (as measured by the SDQ 'difficulties' scale) mediated by parent mentalising, parent anger expression, parent report IPC, child perception of IPC, parenting style, or parent emotional adaptation?

RQ10 Is the effect of MBT-PP (compared to TAU) on wellbeing in children aged 8-14 (as measured by the Stirling Children's Well-being Scale) mediated by parent mentalising, parent anger expression, parent report IPC, child perception of IPC, parenting style, or parent emotional adaptation?

Figure 1. Examining the mechanisms by which MBT-PP may improve children’s externalising and internalising behaviours

[figure not shown]
[figure not shown]

Figure 2. Examining the mechanisms by which MBT-PP may improve children’s psychological well-being

Design

Table 2. Trial design

Trial design, including number of arms		Pragmatic two arm cluster RCT
Unit of randomisation		Family
Minimisation variables (if applicable)		Age group (all CYP aged 8-11 / all CYP aged 12-14 / CYP aged 8-11 and 12-14), Minority ethnic group status of one or both parents (yes / no), relationship status (separated/intact)
Primary outcome	variable	a) Child internalising and externalising
	measure (instrument, scale, source)	a) Parent reported SDQ, total difficulties scale (Goodman, 1997)
Secondary outcome(s)	variable(s)	
 b) Child psychological well-being c) Parent report IPC d) Child perception of IPC e) Parent anger f) Parent mentalising capacity g) Parenting style h) Parent emotional adaptation to separation (separated parents only)
	measure(s) (instrument, scale, source)	
 b) Stirling Children’s Well-being Scale (Liddle & Carter, 2015) c) O’Leary-Porter Scale (Porter & O’Leary, 1980) d) Perceptions of Interparental Conflict-Intensity/Frequency Scale (PIC-I/F) (Kline, Wood & Moore, 2003) e) Dimensions of Anger Reactions- Revised (DAR-R; (Nederlof, Hovens, Muris & Novaco, 2009) f) Parental Reflective Function Questionnaire (Luyten et al., 2009) g) Parenting Scale Short Form (PS-8) (Kliem et al., 2019), a short form of the Parenting Scale (Arnold et al., 1993) h) Emotional Adaptation to Relationship Dissolution Assessment (Millings et al., 2020)

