Baseline for primary outcome	variable	Scores at baseline (pre-randomisation) on variables listed above
	measure (instrument, scale, source)	As above
Baseline for secondary outcome	variable	Scores at baseline (pre-randomisation) on variables listed above
	measure (instrument, scale, source)	As above

Randomisation

Randomisation will be conducted on all consenting referrals (referral and consent procedure are outlined below) as they occur. Because recruitment will be rolling, classic random stratification is not feasible. We will therefore use minimisation (Scott et al., 2002; Altman & Bland, 2005) whereby allocation is random initially and then systematic to minimise differences between groups across a few specified strata within LAs, specifically, child age, parent minority ethnic group status, and relationship status (intact or separated). In the context of rolling recruitment, a minimisation approach will best ensure that the MBT-PP and TAU samples are comparable in terms of the specified strata. The minimisation will be undertaken using the MininPy software.

Participants

Participants will be referred to the project by LA staff (e.g., Early Help practitioners) through an online form. LA staff will be provided with information/training about the project detailing that it is for:

- Parents experiencing high intensity, frequent and unresolved IPC, who have at least one child aged between 8 and 14 years old
- They do not have to live together, or be in a current relationship, but should be willing to think about how they can improve their relationship with their co-parent.
- Parents will need to consent to the referral being made and have an understanding that the work will focus on the quality of the relationship with their co-parent.
- Parents must understand that:
 - This is a research project

- They will be randomly allocated to receive either support from Early Help which will involve using an online therapeutic resource or the MBT-PP intervention, which is delivered online.
- They will need to fill in questionnaires before the start, at the end, and then three months after they finish.
- They will receive vouchers to thank them for their time, once they have completed all the questionnaires.
- They will need to be willing and able to attend either 10 sessions of MBT-PP therapy or engage with the digital resources as directed by Early Help staff

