Referrals will be received by the Gateway Lead (GL), who will review the referral and contact the family. Parents may also self-refer to the project by contacting the GL directly. The GL will administer the DAS-4 (in the case of self-referrals only) and screen for risk (exclusion criteria) with each parent separately.

Inclusion criteria

- Parents must have at least one child aged 8 (or turning 8 during the intervention period, i.e., not more than 16 weeks younger than 8 years) -14 (or still 14 at recruitment).
- Parents must either have been referred for support with interparental conflict by a local authority practitioner (e.g., Early Help staff) or must be classified as a distressed couple on the DAS-4 with one or both parents scoring <13.

Exclusion criteria

- Current issues with substance or alcohol misuse in either parent.
- Significant mental health diagnosis which is not currently well-managed. Further guidance will be provided by Tavistock Relationships to the GLs regarding how to define 'well-managed'.
- Current domestic abuse or violence. (If there are historic issues of domestic abuse / intimate partner violence this should be detailed in the referral.)
- Current engagement in court proceedings (e.g., care proceedings or private family law proceedings).

If inclusion/exclusion criteria permit, the GL will administer the consent procedure and ensure completion of baseline measures.

Consent procedure

The GL will explain the research project and provide participant information sheets and consent forms to parents. This process may take place in person, by phone/email, or online – to be decided in consultation with LA colleagues during the project inception phase. Once consent has been completed for both parents, the GL will assign ID numbers and send each

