parent participant a link to an online questionnaire containing the baseline measures. Children (aged 8-14) of consenting parents will be supported to complete the child outcome measures by the Early Help practitioners and/or the GL, to be decided in consultation with LA colleagues. Children will be asked for their assent prior to completion of these measures. The GL will inform the research team that a new family is ready for randomisation, and the research team will check the secure online survey platform hosting all measures and randomise when the baseline measures have been completed, informing the GL of the outcome of the randomisation. The GL will then inform the relevant team (TR or Early Help), so that contact can be made with the family. Referral data (case details) and contact details will be detached and replaced by ID numbers, and communications between the GL and relevant intervention teams will be via secure (e.g. encrypted or password protected) means.

The theory of change for MBT-PP indicates that the intervention will be maximally effective when both parents engage. As such, the trial is designed based on recruitment of both parents into the trial. However, while the GL will attempt to engage both parents in the trial, should one parent be willing to engage while the other appears unwilling to consent or complete the baseline measures, the family will be accepted into the trial, randomised to one of the two conditions, and the engaging parent will begin their intervention. The GL will contact the other parent 1-2 more times at around week 3, using multiple methods where possible (phone, email, text), to invite them again to participate in the trial. Parents who join the trial (consent and complete baseline measures) at this point will be allocated to the same condition as their co-parent, and in the case of families in the MBT-PP arm, will be invited to join their co-parent for the remaining therapy sessions. In our dataset, we will record which families began the trial with both parents involved, which families had the second parent join part-way through the intervention period, and which families only had one parent engage in the intervention, so that we can conduct sensitivity analyses relating to this.

Intervention delivery

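### The minimisation rule as written has no random element after the start, so it does not protect concealment from the Gateway Lead; how exposed the trial is depends on how local authority entered the algorithm

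*Protocol*

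**What the plan says.** **Rule.** The protocol (Randomisation) states that "allocation is random initially and then systematic to minimise differences between groups across a few specified strata within LAs". The factors are child age group (three levels), minority ethnic status of either parent (two) and relationship status (two). On implementation it says only that "The minimisation will be undertaken using the MininPy software". The SAP (Design overview) adds that the evaluator allocates under a minimisation protocol, whose content is not given. Neither document states an assignment probability, a tie rule, the length of the random phase or the factor weights.

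**Role of LA.** The Randomisation section places the balancing inside LAs. Protocol Table 2, SAP Table 1 and the four minimisation dummies in SAP equation 2.0 do not list LA.

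**Gateway Lead.** The SAP describes one funded post in each of the three LAs. Under the protocol's Participants and Consent procedure sections, the Gateway Lead (GL):
- receives referrals and self-referrals, and must "screen for risk (exclusion criteria) with each parent separately";
- if the criteria permit, continues: "the GL will administer the consent procedure and ensure completion of baseline measures";
- starts the allocation: "The GL will inform the research team that a new family is ready for randomisation";
- hears the result, the research team "informing the GL of the outcome of the randomisation".

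The research team runs the allocation, and only after baseline measures are complete.

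**The concern.** With no random element, every untied allocation after the start follows from the running totals and the new family's three factor values. The GL can know all of these for their own LA while still deciding whether a family enters. Some of those decisions need judgement: whether a mental health condition is adequately controlled, whether the second parent is unlikely to take part, and when to report the family as ready.

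Foreknowledge at that stage allows selection. Parents know which support they receive and the mother reports the primary outcome, so concealed allocation is one of the trial's main protections. The SAP (Analysis) rests its causal claim on all other group differences being random at baseline, and that depends on concealment. Equation 2.0 adjusts for baseline SDQ total difficulties and the minimisation dummies. It cannot adjust for features that a GL might weigh and nobody measures, such as motivation or likely engagement.

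**Working it through.** The documents give no figure for predictability, so there is none to reproduce. The check is a Monte Carlo simulation of the described rule.

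**Inputs from the documents**
- Three factors with 3, 2 and 2 levels (Protocol Table 2); 1:1 allocation.
- 250 families (SAP) or 350 (protocol) in three LAs: 250/3 ≈ 83 or 350/3 ≈ 117 per LA.

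**Assumptions**
- Equal factor weights, ties broken at random, LAs of equal size.
- Three sets of factor frequencies. The base set is age bands 45/35/20%, minority status 20%, separated 60%. The others are an even set and a skewed set.
- Initial random phase of 10 families, with 1, 5 and 20 also tried for the base set.
- The GL sees only own-LA factor values and past allocations, and guesses the arm that lowers imbalance.

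**Rule.** For a new family, let D_k be the current difference in counts (MBT-PP minus TAU) at its level of factor k. Compare Σ|D_k + 1| (if allocated to MBT-PP) with Σ|D_k − 1| (if allocated to TAU). The smaller sum wins with probability p. A tie is split 50:50. The rule as written is p = 1.

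**Link between ties and guessing.** When the GL's totals are the totals that the algorithm uses, the proportion guessed correctly = d × p + (1 − d) × 0.5, where d is the untied share.

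| Setting (250 families, separate minimisation in each LA, base set) | d | Formula | Simulated |
|---|---|---|---|
| p = 1 | 0.782 | 0.782 + 0.218 × 0.5 = 0.891 | 89% |
| p = 0.8 | 0.808 | 0.808 × 0.8 + 0.192 × 0.5 = 0.742 | 74% |
| p = 0.7 | 0.836 | 0.836 × 0.7 + 0.164 × 0.5 = 0.667 | 67% |
| Simple randomisation | – | – | 50% |

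At p = 1, correct guesses ranged only from 88.6% to 89.2% across 250 or 350 families, the three frequency sets and the four lengths of random phase.

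**Sensitivity to the role of LA (p = 1, GL using own-LA records)**

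| How LA enters | Correct guesses |
|---|---|
| Separate minimisation in each LA | about 89% |
| LA as one factor in a trial-wide minimisation | 57% to 62% |
| LA not used | 52% to 53% |

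**Sensitivity to families pending together.** This used one LA, 83 families, the first four random, minority status 17% and separated 50%. The number pending is an assumption.

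| Earlier families in that LA not yet allocated | Using known allocations only | Also predicting the pending families, in order |
|---|---|---|
| 0 | 89% | 89% |
| 1 | about 64% | about 83% |
| 3 | about 57-58% | about 76-77% |

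**Without a full tally.** In the same one-LA setting with none pending, guessing the opposite of the last allocation is right about 67% of the time. Guessing the arm that is behind overall is right about 70%.

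**The case against.** The strongest reply is that the documents are silent rather than wrong. One sentence summarises minimisation, the software may have been run with a probability below 1, and the evaluator's minimisation protocol is not in the public documents. This stands in part: the setting actually used is unknown. A reader might infer that allocations were in fact predictable, or that a GL used foreknowledge. The documents support neither. They support only the statement that the rule they describe leaves concealment exposed.

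Second, a reader might take 89% as the trial's predictability. It is a conditional upper case. It needs separate minimisation in each LA, which the Randomisation text implies but the tables and SAP dummies do not list. It also needs prompt allocation and a GL who keeps a running tally. Randomisation waits for parent questionnaires, supported child measures and a research-team check, so families may well be pending together. This objection stands.

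Third, there are safeguards. Allocation is central and follows baseline. A practitioner's referral for interparental conflict itself meets the conflict criterion, and guidance is promised on the exclusion that most needs judgement. The model also adjusts for baseline SDQ at both levels, with pilot R² of 0.75 (child) and 0.61 (family), so selection on measured severity would be largely absorbed. All this narrows the risk. Central allocation after baseline does not stop a GL from inferring the next arm during screening, and the adjustment does not reach unmeasured traits.

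Fourth, it may be late. The protocol's Timeline ends efficacy baseline collection in December 2024 and SAP version 1.1 is dated 17/01/25. Few or no families may remain, which moves the weight of the remedy towards disclosure.

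**Conclusion.** The point holds for the rule as written. The Randomisation section describes allocation that becomes systematic after a random start, and neither document adds a random element. The same person in each LA screens, consents, reports readiness and learns the result. Run separately in each LA, that rule fixes about 77-78% of later allocations and lets a GL with no families pending guess about 89% correctly. The figure is about 60% if LA is one factor in a trial-wide minimisation, about 53% if LA is unused, and lower with families pending.

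These results rest on assumed factor frequencies, equal weights, random ties and equal LA sizes. The result for separate minimisation in each LA barely changes with the frequencies tried. It changes a great deal with the role of LA and the number pending, and the documents settle neither. The size of any resulting bias in the SDQ effect cannot be estimated from them.

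**What to change.** 1. **Families still to be randomised, if any:** assign each to the imbalance-reducing arm with a stated probability below 1. With minimisation inside LAs, 0.8 lowers correct guesses to about 74% and 0.7 to about 67%.
2. **Protocol and SAP:** state the probability, tie rule, length of the random phase and role of LA actually used so far. Reconcile the Randomisation text with Protocol Table 2, SAP Table 1 and the SAP minimisation dummies on whether LA was part of the minimisation.
3. **If allocation so far was deterministic within LAs:** split by LA the baseline SDQ total difficulties comparison already planned in the SAP (Imbalance at baseline), and report the predictability as a limitation. Families who refused or were found ineligible before randomisation have no allocated arm, so any check on them must use the arm predicted at screening.

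The cost is a change to the allocation rule for any remaining families and a few sentences in each document. The downside is slightly looser balance on three factors that the primary model already adjusts for. If recruitment has closed, only items 2 and 3 apply.
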